Study Protocol and Statistical Analysis Plan

Document Title: Therapeutic Effects of Kinesiotape in the Management of Gonarthrosis: A Randomized Controlled Approach

NCT Number: NCTXXXXXXXX

Document Date: November 25, 2015

Study Protocol

Study Design

This study is a single-blinded, randomized controlled trial involving 38 individuals diagnosed with gonarthrosis according to ACR classification criteria. Participants are randomly assigned to two groups. Taping group (n=19) received kinesiotape application and a home exercise program, while participants in the control group (n=19) received only a home exercise program

Inclusion Criteria

- Having a diagnosis of primary gonarthrosis according to ACR classification criteria,
- Being between 45 and 65 years of age,
- Having a radiological diagnosis of gonarthrosis between Kellgren-Lawrence stage 1-3,
- Signing the informed consent

Exclusion Criteria

- Presence of a neurological disorder affecting muscle strength or balance,
- History of any surgical operation on the knee, hip, or spine,
- Physiotherapy or injections for the knee within the previous year,
- Presence of systemic conditions such as diabetes mellitus, vertigo, visual problems,
- History of severe trauma within the previous year

Interventions

In the taping group, the Mechanical correction technique and the Ligament/Tendon correction technique were applied using kinesiotape application. The taping procedure was repeated once a week, starting from the first week, for a total of 6 sessions. An individualized home exercise program was planned, considering EULAR and ACR recommendations. Each participant was given a structured home exercise program at least 3 days a week. The program included moderate-intensity aerobic exercises (e.g., walking) and muscle-strengthening exercises targeting the quadriceps and hamstring muscles, along with flexibility and balance exercises.

Outcome Measures

The demographic characteristics (age, gender, education, body mass index) were documented for both groups. The patients were evaluated two times with clinical assessment scales: Visual Analogue Scale (VAS) was used to assess pain, Western Ontario and McMaster Universities Osteoarthritis Index (WOMAC) questionnaire to assess pain, stiffness and functionality, Berg Balance Scale (BBS) to assess balance, Short Form (SF-36) to assess physical function,

physical role, emotional status, social function, general health, mental health, pain, quality of life.

Statistical Analysis Plan

Sample size was calculated using G-Power 3.1.3 software. The power and “>” levels were set to 0.80 and 0.05, respectively, and the effect size (ES) was set to 0.8. A priori analysis for the required sample size indicated that at least 21 subjects would be needed in each group. Thus, 23 subjects were used in each group to account for dropout cases (Cohen, 1992). The Kolmogorov-Smirnov and Shapiro-Wilk tests were used to determine whether the obtained measurements conformed to normal distribution, and the data were found to be normally distributed. Since the data were normally distributed, parametric tests were used in the comparisons. Whether there was a significant difference between the averages of these parameters measured before and after the treatment between the control and taping groups was analyzed by a t-test in independent groups, and whether there was a significant change between the parameters before and after the treatment in the taping and control groups separately was analyzed by a t-test in dependent groups. The change in parameters from pre-treatment to post-treatment was also analyzed for significant differences between groups using a t-test in independent groups. The data obtained in the research were analyzed using the SPSS (Statistical Package for Social Sciences) for Windows 20.0 program.

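### The protocol reports 38 participants (19 per group), but the SAP says at least 21 per group were needed and 23 were used; if 19 is right, the trial is below its own minimum.

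*Combined protocol and SAP*

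**What the plan says.** The protocol's Study Design section presents a "randomized controlled trial involving 38 individuals diagnosed with gonarthrosis according to ACR classification criteria", says that they are randomly assigned to two groups, and gives the sizes with the treatment received: "Taping group (n=19) received kinesiotape application and a home exercise program", and "participants in the control group (n=19) received only a home exercise program".

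The Statistical Analysis Plan opens with the sample size. Power and significance level (the symbol for the latter is garbled in the text) come first: "levels were set to 0.80 and 0.05, respectively, and the effect size (ES) was set to 0.8". Then: "A priori analysis for the required sample size indicated that at least 21 subjects would be needed in each group". Then: "Thus, 23 subjects were used in each group to account for dropout cases". The between-group comparisons are by independent-groups t-test and the within-group comparisons by dependent t-test. Whether any of these tests is one-sided or two-sided is not stated.

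**The concern.** Both statements are current text of one combined document, and they cannot describe the same set of participants. The SAP reports 23 per group as what was used, not only as a target, and the protocol attaches 19 per group to the randomised groups. Three readings are possible:

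- **(a)** 19 per group is the randomised or analysed size. The trial then falls short of the SAP's minimum.
- **(b)** 23 per group is right. The minimum is met, and the Study Design section misstates the size of the trial.
- **(c)** 46 were randomised and 38 completed. The Study Design section then presents completers as if they were the randomised groups.

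The documents do not settle which applies. Every t-test in the SAP depends on this number. Under (c) the comparisons would be completer analyses, with losses that no reader could see or assess.

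**Working it through.** **Inputs.** Study Design: 38 in total, 19 and 19. SAP: effect size 0.8, significance level 0.05, power 0.80, minimum 21 per group, 23 per group used. Assumption: the calculation was for an independent-groups t-test with equal groups. The SAP does not name the test at that point, but a requirement stated per group, and the later between-group t-tests, point that way. Sidedness is not given, so both are shown.

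**Counts.**
- 2 × 19 = 38, which agrees with the protocol's total.
- 2 × 21 = 42 and 2 × 23 = 46.
- 46 − 38 = 8 participants unexplained.
- 21 − 19 = 2 per group below the minimum; 23 − 19 = 4 per group below the number said to be used.

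**Reproducing the SAP's 21.** For n per group and standardised effect d, the test has 2n − 2 degrees of freedom and noncentrality d × √(n/2). Power is the probability that a noncentral t with these parameters passes the critical value: t(0.95, 2n − 2) one-sided, t(0.975, 2n − 2) two-sided.

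Example, n = 19: noncentrality 0.8 × √9.5 = 2.466 on 36 df. The critical value is 1.688 one-sided (power 0.781) and 2.028 two-sided (power 0.670).

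| n per group | Power, one-sided | Power, two-sided |
|---|---|---|
| 19 | 0.781 | 0.670 |
| 20 | 0.799 | 0.693 |
| 21 | 0.817 | 0.716 |
| 23 | 0.848 | 0.756 |
| 25 | 0.874 | 0.791 |
| 26 | 0.885 | 0.807 |

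One-sided, 21 is the smallest size that reaches 0.80, so the SAP's figure is reproduced exactly. Two-sided, the smallest size is 26.

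**Effect detectable with 80% power** (the same formula solved for d):

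| n per group | One-sided | Two-sided |
|---|---|---|
| 19 | 0.82 | 0.93 |
| 21 | 0.78 | 0.89 |
| 23 | 0.74 | 0.84 |

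**How much of the shortfall comes from the size conflict.**
- One-sided at 19: 80.0 − 78.1 = 1.9 points.
- Two-sided at 19: 80.0 − 67.0 = 13.0 points. Of these, 71.6 − 67.0 = 4.6 come from having 19 instead of 21. The other 80.0 − 71.6 = 8.4 would remain at 21 and come from sidedness.

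**Precision.** The expected 95% confidence interval half-width for a group difference, in SD units, is t(0.975, 2n − 2) × √(2/n):
- 19 per group: 2.028 × 0.3244 = 0.66.
- 23 per group: 2.015 × 0.2949 = 0.59.

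**Does dropout explain it?** Going from 21 to 23 allows for 2/23 = 8.7% loss. Going from 46 to 38 would be 8/46 = 17.4%, twice the allowance, and would still leave 19 per group against a minimum of 21.

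**The case against.** The strongest defence is that 46 were enrolled and 38 completed, so that each section is right about a different count. Neither section says so, and the protocol ties 19 per group to random assignment and treatment received. Even if it were true, the analysed groups would be below 21. This does not rescue the text.

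A second objection is that the power consequence is slight. On the only basis that reproduces the SAP's own figure, the loss is 1.9 points and the detectable effect moves from 0.80 to 0.82. The larger two-sided shortfall is mostly a separate matter, since 8.4 of its 13.0 points would be there with 21 per group. This stands. The seriousness of the point rests on the unknown numbers randomised and analysed, not on lost power. Sidedness still has to be stated, because power at any reconciled size cannot be given without it.

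A third objection is that the SAP never names the test behind the sample size, so the statement that 21 is reproduced only by a one-sided test depends on taking it to be an independent-groups t-test. This also stands: the inference is likely, but the sponsor should confirm it.

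**Conclusion.** The concern holds, and the text is wrong as written. The size of the trial is stated as 38 in one section and 46 in another, with no reconciliation. If 19 per group is the analysed size, whether by design or through losses, it is 2 per group below the SAP's minimum and the stated 80% power does not hold: it is 78.1% one-sided or 67.0% two-sided. If 23 per group was analysed, power is 84.8% one-sided but only 75.6% two-sided, so restoring 23 would not by itself give 80% for two-sided tests. The conflict between the counts rests on no assumption. The power figures assume an independent-groups t-test, effect size 0.8 and significance level 0.05.

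**What to change.** 1. Replace the two statements with one set of numbers for each group: randomised, completed and analysed.
2. Keep the a priori calculation on record and complete it, for example: *[independent-groups t-test, to be confirmed], effect size 0.8, significance level 0.05 [one-sided / two-sided], power 0.80, 21 per group*.
3. Beside it, state power and detectable effect at the size actually analysed, for the confirmed sidedness, or for both if it cannot be confirmed. For 19 per group: 78.1% and 0.82 one-sided, 67.0% and 0.93 two-sided. For 23 per group: 84.8% and 0.74 one-sided, 75.6% and 0.84 two-sided.
4. Report group differences with 95% confidence intervals, which show the precision achieved. If the tests prove to be one-sided at 0.05, note that a 95% interval does not match that test.
5. Only if it is confirmed that 46 were randomised and 38 completed: report the 8 losses by group, label the 38-participant t-tests as a completer analysis, and add a sensitivity analysis for the missing post-treatment values that includes missing not at random.

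The cost is wording in the protocol and SAP, possibly a less favourable power figure, and at most one extra sensitivity analysis. No new patients are required.

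### Allocation concealment is not described, the patient-rated baseline is not placed before allocation, and Kellgren-Lawrence grade is neither a stratum nor a covariate

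*Combined protocol and SAP*

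**What the plan says.** Study Design calls the trial single-blinded: "This study is a single-blinded, randomized controlled trial involving 38 individuals diagnosed with gonarthrosis according to ACR classification criteria". The sentence on allocation reads "Participants are randomly assigned to two groups". The arms are "Taping group (n=19) received kinesiotape application and a home exercise program" and "participants in the control group (n=19) received only a home exercise program". Nothing in the protocol or SAP describes how the sequence was generated, who held it, how it was concealed, or whether blocks or strata were used. Nor do they say which party was blinded, and no sham tape is described.

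Inclusion Criteria admit three radiographic grades: "Having a radiological diagnosis of gonarthrosis between Kellgren-Lawrence stage 1-3". The grade is therefore known for every patient at entry, but it appears nowhere else in the plan.

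Outcome Measures says "The patients were evaluated two times with clinical assessment scales". The SAP ties these two evaluations to treatment, in comparing "averages of these parameters measured before and after the treatment between the control and taping groups". It also compares pre-to-post change between arms with an independent-groups t-test and names no covariate.

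The SAP gives a different arm size from Study Design: "23 subjects were used in each group to account for dropout cases".

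**The concern.** Patients in this comparison can see whether they are taped, and whoever applies the tape each week knows the arm. A blinded assessor would protect the observer-rated balance scale, but would neither hide the next assignment from the person enrolling nor mask patients who rate their own pain, function and quality of life. That makes two unstated safeguards important.

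1. **Concealment.** Without it, a recruiter who knows or can guess the next assignment can influence who enters which arm.
2. **Order of baseline and allocation.** A baseline taken before treatment can still be taken after the patient has learned the arm. Any arm-related shift in that rating is then subtracted from the follow-up score and enters the change contrast in full.

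KL grade is a lesser matter. Leaving a known severity grade out of both design and analysis, in a trial this small, leaves its balance to chance and forgoes whatever precision it could give.

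**Working it through.** The plan gives no figure on allocation to reproduce. The SAP's sample-size calculation does not bear on this point. The calculations below show size only, and their assumed inputs are marked.

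**1. What equal arms tell us.** Under simple randomisation, P(exactly equal arms) = C(N, N/2) / 2^N.
- N = 38 (19 + 19, Study Design): 0.129
- N = 46 (23 + 23, SAP): 0.117

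Equal arms are somewhat unusual under simple randomisation but compatible with it.

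**2. Baseline rated with knowledge of the arm.** Inputs: n = 19 per arm (Study Design); two-sided 5% test with 36 degrees of freedom (sidedness is not stated, so two-sided is assumed); between-arm shift b in the baseline rating of 0.2 or 0.3 SD (assumed); pre-post correlation r of 0.3, 0.5 or 0.7 (assumed); equal SD at both times, no true effect and no shift at follow-up (assumed).
- Bias in the change contrast has size b.
- SD of change = √(2(1 − r)), in units of the single-measurement SD.
- Noncentrality = b / [SD of change × √(2/n)]. For r = 0.5 and b = 0.3: SD of change = 1.00, √(2/19) = 0.324, noncentrality = 0.3/0.324 = 0.92.

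| r | b = 0.2 | b = 0.3 |
|---|---|---|
| 0.3 | 0.080 | 0.118 |
| 0.5 | 0.092 | 0.147 |
| 0.7 | 0.121 | 0.213 |

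Entries are the type I error of the change-score t-test (nominal 0.05). A baseline-adjusted analysis (ANCOVA) would carry bias r × b, from 0.3 × 0.2 = 0.06 to 0.7 × 0.3 = 0.21 SD. That is smaller than b but not zero.

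**3. Chance imbalance in KL 3.** Inputs: 38 patients split 19/19 (Study Design); K of them KL 3, with a share of roughly 30 to 50% (assumed, because the plan gives no mix); no stratification. The number of KL 3 patients in one arm is hypergeometric(38, K, 19). A gap of 20 points needs 0.20 × 19 = 3.8, so at least 4 patients. The gap has the same parity as K, so an odd K needs a gap of at least 5 and an even K a gap of at least 4.
- Odd K (11, 13, 15, 17, 19): 0.15 to 0.19
- Even K (12, 14, 16, 18): 0.30 to 0.33

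Treating the arms as independent binomials instead gives 0.227 (share 1/3) and 0.256 (share 1/2), between the two sets. At 23 per arm the binomial figures are 0.158 and 0.184. The result depends on the 20-point cut, so about 15 to 33% is the fair statement.

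**The case against.** The strongest objection is that this point rests on silence. Several stronger readings are tempting, and the documents do not support them.

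- A reader might infer an open trial. Study Design says single-blinded, and a blinded assessor is quite possible. What stands is that the blinded party is not named and that patients can hardly be blind to tape versus no tape.
- A reader might infer that allocation was not concealed. The documents say nothing either way; concealment is undescribed, not shown to be absent.
- A reader might infer small, predictable blocks from 19/19. Simple randomisation gives that split in 13% of trials, and drawing 19 of 38 lots gives it every time. Since the SAP says 23 per group, 19/19 may also be an analysed count rather than a randomised one.
- The SAP does put the first evaluation before treatment, and a baseline rated after allocation is only a possibility. This is fair, but before treatment does not mean before allocation, and no other text closes the gap.
- Stratification by KL grade can be called a preference. No figure in the documents links KL grade to change in any outcome, so the gain in precision cannot be quantified. This stands, and it is why the KL element carries less weight.
- The SAP reports that the data were found to be normally distributed, so recruitment may be over and the design changes too late. Reporting and adjustment would remain possible.

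**Conclusion.** The point holds as a gap in described safeguards, not as a demonstrated bias. The plan describes no concealment, names no blinded party, and does not place the patient-rated baseline before allocation, although that rating is subtracted in an unadjusted test. If the baseline was rated with knowledge of the arm, an assumed shift of 0.2 to 0.3 SD would pass in full into the contrast and raise the type I error to about 8 to 21%. ANCOVA would reduce this bias but not remove it. Selection at enrolment is not something that later analysis can be relied on to undo.

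A reader might also infer that missing stratification biases the comparison. It does not: under proper randomisation it leaves chance imbalance and lost precision. With 19 per arm and 30 to 50% KL 3 (assumed), a gap of at least 20 points has a probability of about 15 to 33%.

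This should be changed because the remedy is cheap. Confidence is medium, since the safeguards may have been in place but not written down.

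**What to change.** **If allocation has not finished**
- State that the first evaluation is completed and locked before the patient's allocation is opened.
- Conceal the list from the person enrolling, and say how and by whom it is held. Name the blinded party.
- Stratify by KL grade (1-2 versus 3), with randomly varying block sizes that are undisclosed and not limited to the smallest sizes. For 38 patients, a recruiter who always guesses the under-filled arm is right about 72% of the time with a random mix of blocks of 2 and 4, against 70% for fixed blocks of 4 and 68% for fixed blocks of 6.
- In the SAP, include the KL stratum as a covariate in the between-arm comparison.

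**If allocation is complete**
- Report how the sequence was generated and concealed, who was blinded, and whether baseline preceded allocation.
- Give the KL-adjusted between-arm comparison, labelled post hoc if it was not prespecified.

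**Cost.** A few sentences in the protocol and SAP, minor logistics for the list, and one degree of freedom for the two-level stratum. The stated sample size does not change.

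### No primary outcome, hierarchy or multiplicity adjustment for 13 scores, each with two outcome-bearing between-group t-tests: the chance of at least one false positive is roughly 40–72%

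*Combined protocol and SAP*

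**What the plan says.** Study Protocol, Outcome Measures: "The patients were evaluated two times with clinical assessment scales: Visual Analogue Scale (VAS) was used to assess pain". The section then lists WOMAC (three domains), the Berg Balance Scale and SF-36 (eight items). No score is called primary and no order of importance is given.

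Statistical Analysis Plan: independent-groups t-tests address "Whether there was a significant difference between the averages of these parameters measured before and after the treatment between the control and taping groups". The plan adds: "The change in parameters from pre-treatment to post-treatment was also analyzed for significant differences between groups using a t-test in independent groups". Paired t-tests within each arm are specified as well. There is no hierarchy, no adjustment and no exploratory label, and the parameters are not defined.

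The 0.05 level appears only in the sample-size text: "levels were set to 0.80 and 0.05, respectively, and the effect size (ES) was set to 0.8". That effect size is attached to no score. The sidedness of the tests is not stated.

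The plan also reports a result from the data: "and the data were found to be normally distributed".

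**The concern.** The documents contain no rule for deciding which comparison supports a conclusion about tape. Pain alone is measured three times (VAS, WOMAC, SF-36), and each score gets two between-group tests that bear on the outcome. If every test is read at 0.05, that level describes a single test and not the trial's conclusion. One significant result among 26 could be reported as efficacy.

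The stated 80% power likewise belongs to no particular claim, because the effect size of 0.8 is tied to no outcome.

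**Working it through.** **The plan's own figure.** The plan states "at least 21 subjects would be needed in each group" for effect size 0.8, power 0.80 and level 0.05. The exact noncentral-t calculation for two independent means gives:

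- one-sided 0.05: n = 20.03, rounded up to 21 per group, which matches;
- two-sided 0.05: n = 25.5, rounded up to 26 per group, which does not.

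So the stated size fits a one-sided test, although the plan never says so. The main figures below assume two-sided tests; the one-sided case is shown separately.

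**Counting the tests.** 1 (VAS) + 3 (WOMAC) + 1 (Berg) + 8 (SF-36) = 13 scores. Counting only the post-treatment and change comparisons, 13 × 2 = 26. Baseline comparisons and within-arm paired tests are left out.

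**Benchmarks under independence.** The chance of at least one false positive in k independent tests is 1 − (1 − α)^k.

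- One test per score: 1 − 0.95^13 = 0.487.
- All 26 tests: 1 − 0.95^26 = 0.736; in one direction, 1 − 0.975^26 = 0.482.

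The tests are not independent, so these serve only as reference points.

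**Simulation.** The documents supply the 19 per group, the 0.05, the scores and the tests. These are assumed: no true effect on any score, normal data, two-sided tests, an equal correlation between every pair of scores, and a pre-post correlation of 0.5. The correlation between one score before treatment and a different score after it is taken as the product of the two correlations. There were 40,000 null trials per cell. Each cell gives the chance of at least one false significant result.

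| Reading | Between-score correlation 0 | 0.5 | 0.7 |
|---|---|---|---|
| 13 scores, post or change, either direction | 71% | 54% | 40% |
| Same, favouring tape (nominal 2.5%) | 45% | 28% | 21% |
| Same, favouring tape, one-sided 0.05 tests (nominal 5%) | 70% | 43% | 33% |
| 13 scores, change only, either direction | 49% | 34% | 24% |
| 4 scores (one per instrument), post or change, either direction | 32% | 27% | 23% |
| 4 scores, change only, either direction | 18% | 16% | 13% |

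Sensitivity of the 13-score, post-or-change figures:

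- Pre-post correlation 0.3 to 0.7: 40–72% in either direction, 20–46% favouring tape.
- Between-score correlation 0.8: 33% and 17%.
- 23 per group instead of 19, either direction: 71% / 54% / 41%.
- 12 scores, reading quality of life as the overall SF-36 concept: about 39–69% and 20–44%.

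**A single score.** With equal variances, the post-treatment difference and the change difference correlate at √((1 − r)/2), which is 0.5 at r = 0.5. Accepting whichever of the two tests is significant raises the error for one score from 5% to about 9%.

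**The case against.** The omission itself is hard to dispute. The objections concern its size and what can still be done.

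- **The test count.** Read literally, the plan has three between-group t-tests per score, because pre-treatment values are compared too. That is correct. The baseline test says nothing about efficacy and is excluded here; including it raises the chance of any significant result to about 48–82%.
- **The upper end is unlikely.** The 71–72% figures need unrelated scores, which is implausible with three pain measures. This stands: the middle of the range is the better guide. Even the mildest scenario above, four scores with change tests only at between-score correlation 0.7, gives 13% against 5%.
- **The correlation structure is a choice.** This also stands, but the alternative raises the figure. If the scores share a stable person-level effect, with both correlations at 0.7, the either-direction figure is about 60% rather than about 41%.
- **No success rule is stated.** The percentages describe declaring success on any significant test, and the documents never say that this is the rule. They state no rule at all, which is the defect. The percentages show what the gap permits.
- **It is too late to prespecify.** The data had already been examined, so a primary outcome chosen now is not prespecified unless an earlier record names it. This limits the remedy without removing the problem.

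**Conclusion.** The concern holds. Confidence is high for the omission; the percentages depend on the stated assumptions. With 13 scores, two outcome-bearing tests each and two-sided 0.05 tests, the chance of at least one false significant difference is about 40–72% in either direction and 20–46% favouring tape, for between-score correlations of 0–0.7 and pre-post correlations of 0.3–0.7. If the tests are one-sided, as the sample size suggests, the figure favouring tape is about 33–70% against a nominal 5% (pre-post correlation 0.5). Fewer scores or a single test per score lowers the error, but no multi-score scenario examined brings it back to the nominal level. This must be fixed before any efficacy conclusion is drawn. The plan's two different group sizes (19 and 23) are a separate matter and do not affect this result.

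**What to change.** **If an earlier dated record names the primary outcome.** Cite it. State one between-group test for it, for example post-treatment VAS pain or WOMAC pain adjusted for its own baseline, two-sided 0.05, and attach the power statement to that test. Stop using the paired post and change t-tests as duplicate evidence of efficacy. Holm-adjust the remaining scores, or report them as exploratory with confidence intervals and no efficacy claim. The cost is SAP wording, and a single significant secondary score can no longer carry the efficacy claim.

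**If no such record exists.** Disclose that any choice of primary outcome is post hoc. Then either label all results exploratory, or run one baseline-adjusted test per score with Holm adjustment across all 13. Under the same assumptions, Holm holds the family-wise error at 4.8% / 3.9% / 2.9% for between-score correlations 0 / 0.5 / 0.7.

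The second route costs power. The first Holm step is 0.05/13 = 0.0038. For one score with a true effect size of 0.8 and 19 per group, two-sided power at that step falls from 67% to 29% with a t-test. With baseline adjustment at an assumed pre-post correlation of 0.5, the effective effect size is 0.8/√(1 − 0.25) = 0.92, and power falls from 79% to 42%. Under the exploratory label, the cost is that the trial makes no confirmatory claim.

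On either route, define the list of scores and state the level and sidedness of the outcome tests.

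### The 21 per group matches only a one-sided t-test; sidedness is never stated, a two-sided 0.05 test needs 26, and 19 per group misses 80% power either way

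*Combined protocol and SAP*

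**What the plan says.** The Statistical Analysis Plan gives the inputs as "levels were set to 0.80 and 0.05, respectively, and the effect size (ES) was set to 0.8". The first symbol is garbled in the text and is read here as alpha. The result from G-Power 3.1.3 is "A priori analysis for the required sample size indicated that at least 21 subjects would be needed in each group", and the SAP continues: "Thus, 23 subjects were used in each group to account for dropout cases". It does not name the outcome or the test on which the study was sized.

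The same section plans independent-groups t-tests on the before- and after-treatment averages, dependent-groups t-tests within each arm, and an independent-groups t-test on change. None is given a direction: the first is introduced with "Whether there was a significant difference between the averages of these parameters", and the change from before to after treatment "was also analyzed for significant differences between groups using a t-test in independent groups".

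Study Design, in the Study Protocol, gives other numbers: 38 participants, described as "Taping group (n=19) received kinesiotape application and a home exercise program, while participants in the control group (n=19").

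**The concern.** A calculated sample size should follow from its stated inputs and from the test that will be run. For a standardised difference of 0.8, 80% power and alpha 0.05, a two-sided comparison of two independent groups needs more than 21 per group. So 21 suggests either an error or a one-sided setting that was not disclosed. The choice matters: a one-sided 0.05 test rejects in the favourable direction at the same threshold as a two-sided 0.10 test.

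The 80% power is the only justification offered for the size of the trial. If it does not apply to the between-group test of change, which is the randomised comparison, a reader could take a non-significant result as stronger evidence against a large effect than it is. The 19 per group under Study Design adds to the problem, because it lies below the SAP's own minimum of 21.

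**Working it through.** **Inputs.** From the SAP: power 0.80, alpha 0.05, effect size d = 0.8, independent-groups t-test, stated requirement 21, number used 23. From Study Design: 19 per group, 1:1. Sidedness is given nowhere, so both versions are run. The effect size is read as Cohen's d for the quantity being compared.

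**Formula.** With n per group, df = 2n − 2 and noncentrality δ = d·√(n/2). Power is the probability that a noncentral t variable with this df and δ exceeds the critical value: t(0.95, df) one-sided, or t(0.975, df) two-sided (plus a negligible opposite tail).

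**Reproducing the SAP's 21.**
- One-sided, n = 20: df = 38, δ = 0.8·√10 = 2.530, critical value 1.686, power 0.799.
- One-sided, n = 21: df = 40, δ = 0.8·√10.5 = 2.592, critical value 1.684, power 0.817.

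The exact solution is 20.03, which rounds up to 21. The SAP's figure is reproduced.

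**Same inputs, two-sided.**
- n = 25: df = 48, δ = 0.8·√12.5 = 2.828, critical value 2.011, power 0.791.
- n = 26: df = 50, δ = 0.8·√13 = 2.884, critical value 2.009, power 0.807.

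The exact solution is 25.52, which rounds up to 26.

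**Could the within-group test explain 21?** For the dependent-groups t-test, df = n − 1 and δ = d·√n. It needs 14.30, so 15, two-sided; and 11.14, so 12, one-sided. Neither is 21.

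**Power at each number in the documents (d = 0.8).**

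| n per group | Source | Two-sided power | Two-sided Type II error | One-sided power | Effect detectable with 80% power, two-sided |
|---|---|---|---|---|---|
| 19 | Study Design | 67.0% | 33% | 78.1% | 0.93 |
| 21 | SAP, calculated minimum | 71.6% | 28% | 81.7% | 0.89 |
| 23 | SAP, number used | 75.6% | 24% | 84.8% | 0.84 |
| 26 | two-sided requirement | 80.7% | 19% | 88.5% | 0.79 |

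**Two-sided alpha at which power would reach 80%:** 0.114 at 19 per group, 0.089 at 21 and 0.069 at 23.

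**The case against.** **The 21 is not a miscalculation.** This stands. It is exactly right for a one-sided 0.05 test. The defect is that the assumption behind it is undeclared and does not fit comparisons worded without direction.

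**Two-sided testing is inferred.** This also stands, but the inference is not needed at 19 per group, where one-sided power is 78.1%. That shortfall is only about two percentage points. The two-sided shortfall is 13 points (80% less 67.0%).

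**The effect size may not be on the change-score scale.** The SAP ties 0.8 to no outcome or time point. Suppose it refers to the SD of raw scores, with equal SDs before and after and no expected baseline difference. The standardised effect on change is then 0.8/√(2(1 − r)), where r is the pre–post correlation. The documents give no r, so the following range is an assumption. Two-sided power at 19, 21 and 23 per group is 53%, 57% and 61% for r = 0.3; 67%, 72% and 76% for r = 0.5; 76%, 81% and 84% for r = 0.6; and 87%, 90% and 93% for r = 0.7. The 80% target is reached at r of about 0.63, 0.59 and 0.55 respectively. Power could thus be better or worse than in the table. This limits the power claim to a difference of 0.8 SD in the quantity compared. It does not rescue the stated 21, which was derived from 0.8 itself.

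**Putting 26 in place of 21 could misreport how the study was sized.** This is a fair point about the remedy, and the fix allows for it.

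**The study appears complete and the 19/23 mismatch is a separate inconsistency.** Both are largely true. No patients can be added and no test need change. But the stated power cannot be assessed until the number analysed is known.

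**Conclusion.** The concern holds. With the SAP's own inputs, 21 per group is a one-sided result, five short of the 26 that a two-sided 0.05 test requires. Two-sided, the trial has 67.0% to 75.6% power at the three stated sizes instead of 80%, and the effect it can detect with 80% power is 0.84 to 0.93 instead of 0.8. At the 19 per group in Study Design the claimed power is missed on either reading.

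The arithmetic rests on 1:1 allocation and on 0.8 being the standardised difference in the quantity compared. The three-size statement also rests on two-sided testing, which the wording of the analyses implies but does not state. The paragraph must be corrected, because its power claim is wrong as it stands and is the sole justification for the sample size.

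**What to change.** 1. State that all tests are two-sided at 0.05, and disclose the tail setting entered in G-Power. If 21 came from a one-sided setting, say so, so that the record of how the study was sized stays accurate.
2. Give the requirement that matches the analysis. Suggested wording: *For 80% power at an effect size of 0.8, an independent-groups t-test at two-sided alpha 0.05 needs 26 participants per group.* Name the outcome and quantity to which the 0.8 applies.
3. Reconcile the 19 per group in Study Design with the 21 and 23 in the SAP, saying how many were planned, randomised and analysed. The SAP's allowance is 2 of 23 (8.7%). If 19 are those who remained of 23, the loss was 4 of 23 (17.4%), but the documents do not say so.
4. At the reconciled number analysed, report two-sided power and detectable effect: 67% and 0.93 at 19 per group, 72% and 0.89 at 21, or 76% and 0.84 at 23. Confidence intervals for the between-group differences would serve readers better still when the results are interpreted.
5. If a one-sided test was in fact prespecified, say so, give its direction and justify it. Power at 19 per group is then 78%, still below 80%.

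The cost is a rewritten sample-size paragraph, group sizes that agree across the document, and a less favourable stated power. No enrolment is added, and no estimate or test changes if the analyses were run two-sided.
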